#### **15.0 TERMINATION OF THE STUDY**

For reasonable cause, either the investigator or the sponsor, Terumo BCT, may terminate the investigator's participation in this protocol, provided a written notice is submitted within the time period provided for in the Clinical Study Agreement. In addition, Terumo BCT may terminate the Protocol at any time upon immediate notice for any reason.

## **16.0 PUBLICATION POLICY**

Terumo BCT recognizes the importance of communication of medical Protocol data, and encourages the publication of such data in reputable scientific journals and the presentation of such data at scientific seminars and conferences. Any proposed publication or presentation of the data generated from the Protocol must be provided to Terumo BCT for timely review in accordance with the terms of the agreement between the investigator, the Institution, and Terumo BCT. Terumo BCT shall not, in its scientific publications or promotional material, quote from publications by investigator without full acknowledgment of the source.

## **17.0 CONFIDENTIALITY**

All information provided to the investigator by Terumo BCT, including nonclinical data, retrospective data collection protocol, and verbal and written information, will be kept strictly confidential and confined to the clinical personnel involved in conducting this study, and no disclosure shall be made except in accordance with any right of publication granted to the investigator. All personnel will handle patient data in a confidential manner in accordance with applicable regulations governing clinical research. This information may be related in confidence to the EC or other committee functioning in a similar capacity. In addition, no reports or information about the Protocol or its progress will be provided to anyone not involved in the Protocol other than to Terumo BCT, or in confidence to the EC or similar committee, except if required by law.

## AMENDMENT 1.0 SUMMARY OF CHANGES

Protocol Title:	Multicenter, Retrospective Data Collection of Routine Clinical Use with the Spectra Optia® Apheresis System for White Blood Cell Depletion
Protocol Number:	CTS-5043
Version/Date:	Original version 1.0/18 Feb 2014 Amendment 1.0/28 Sep 2016
Rationale:	This amendment adds to the protocol original version 1.0, dated 18 February 2014.  This amendment was made to address regulatory agency feedback and to extend the duration of safety data collection following the apheresis procedure.
Changes from Original Version 1.0:	Previously during this retrospective study, safety data were collected during the White Blood Cell Depletion (WBCD) apheresis procedure and for up 2 hours post-procedure.  With this amendment, safety data (eg, adverse events [AE], blood product transfusions, and clinical laboratory results, as available) will be collected for the 24-hour time period following the WBCD procedure. No other changes are made to study conduct, subject enrollment, or data analysis.

## SYNOPSIS

Protocol Title:	Multicenter, Retrospective Data Collection of Routine Clinical Use with the Spectra Optia® Apheresis System for White Blood Cell Depletion
Protocol Number:	CTS-5043
Target Population:	Patients who have undergone WBCD via the Spectra Optia Apheresis System which is likely to include patients with severe leukocytosis in acute leukemia (acute myeloid leukemia [AML], acute lymphoblastic leukemia [ALL], or in chronic myeloid leukemia [CML]) or to prevent tumor lysis syndrome.
Device Description:	The Spectra Optia System for WBCD is comprised of (1) hardware (the actual apheresis machine) and a removable centrifuge filler (2) a sterile single-use disposable tubing set (the Spectra Optia IDL set) and (3) embedded software V7.2 or higher for WBCD.
Intended Use:	The Spectra Optia Apheresis System, a blood component separator, is intended for use in therapeutic apheresis and cell collections and may be used to perform WBCD.
Objective:	To gather a broader knowledge and information from routine clinical use on the performance and safety of WBCD via the Spectra Optia Apheresis System.
Outcome Measures:	

Percent decrease in white blood cell (WBC) count in patient blood following apheresis procedure.

Percent of processed WBC which are collected, i.e. Collection efficiency for WBC achieved by Spectra Optia.

Adverse events during the WBCD apheresis procedure and for up 24 hours post-procedure.

Inclusion Criteria:	Patients having received a minimum of 1 WBCD procedure via the Spectra Optia Apheresis System.
Protocol Design:	This is a multicenter, retrospective data collection to evaluate the in routine use performance and safety of WBCD performed via the Spectra Optia Apheresis System.
Data Collection Duration:	Routine use data will be collected retrospectively from November 2011 to December 2013.
Statistical Methodology:	Patient demographics and performance parameters will be summarized with the mean, standard deviation, median, and range for continuous variables and with frequencies and percentages for discrete variables.

## LIST OF ABBREVIATIONS

ALL	Acute lymphoblastic leukemia
AML	Acute myeloid leukemia
AE	Adverse Event
CML	Chronic myeloid leukemia
CRF	Case Report Form
EC	Ethics Committee
INR	International Normalized Ratio
PT	Prothrombin time
SAE	Serious Adverse Event
WBC	White blood cell
WBCD	White blood cell depletion

## 1.0 INTRODUCTION

White blood cell depletion (WBCD) by apheresis procedures have been conducted in patients for the past 30 years to rapidly reduce the concentration of white blood cells (WBCs) that have proliferated to levels in the circulation that could cause serious injury. However, these depletion procedures are practiced infrequently and are performed emergently in patients at risk of life-threatening complications due to high WBC counts. For these reasons, prospective, controlled trials are not feasible and have not been done.

The purpose of this retrospective data collection is to gather routine use data to further support the use of the Spectra Optia Apheresis System for WBCD procedures, which has been in clinical use in Europe since November 2011. Additionally, the objective of this retrospective data collection is to gather a broader knowledge and information from routine clinical use on the performance and safety of WBCD via the Spectra Optia® Apheresis System.

### 1.1 Rationale for Amendment 1.0

The protocol original version 1.0 (dated 18 Feb 2014) was conducted and the device performance and safety data were summarized, including retrospective safety data for 2 hours following the apheresis procedure. Upon consideration of study results by the US Food and Drug Administration, regulators requested retrospective safety data not just for the 2 hours following the apheresis procedure, but also for the full 24 hours following the apheresis procedure.

This amendment was made to address regulatory agency feedback and to extend the duration of safety data collection following the apheresis procedure. With this amendment, safety data (eg, adverse events [AEs], blood product transfusions, and clinical laboratory results, as available) will be collected for the full 24-hour time period following the WBCD procedure, as requested by the US Food and Drug Administration. Under protocol version 1.0 (dated 18 Feb 2014), safety data were collected for the first 2 hours following apheresis; this amendment will collect safety data in the 22-hour time period from 2 hours postapheresis until 24 hours postapheresis.

This protocol amendment does not make changes to any of the following topics defined in the protocol original version (dated 18 Feb 2014): the study population, the definition of AEs and serious adverse events (SAEs), AE characterizations (eg, severity, action taken, relationship, outcome, SAE criteria), data analysis, or study management procedures.

This amendment does collect the following new information:

- Collection of AEs in the 22-hour time period from 2 hours postapheresis until 24 hours postapheresis
- Additional characterization of AE relationship to underlying disease or treatment for underlying disease (eg, chemotherapy)
- Reason for transfusion of blood products, if transfusions were administered in the 24-hour period postapheresis
- Postapheresis clinical laboratory results, as available

## **2.0 DATA COLLECTION**

### **2.1 Ethics Committee**

The Institution's Ethics Committee (EC), or other committee functioning in a similar capacity, will review and approve the retrospective data collection protocol amendment. After approval by the EC, documentation of approval will be sent to Terumo BCT before any data are collected for this study.

### **2.2 Informed Consent**

Obtaining patient consent retrospectively and in this very sick patient population is not feasible. Therefore, to protect patient privacy, patient identifier information (e.g., name, initials, birth date, and race) will not be collected in this retrospective data collection study. An EC waiver to collect these de-identified data will be obtained.

### **2.3 Data Handling and Record keeping**

All required data for this protocol will be gathered from subject medical records and recorded in unique Case Report Forms (CRFs) designed to specifically capture safety data for the 24-hour time period following the WBCD procedure. All data must be recorded in English.

### **2.4 Data for Collection**

Clinical routine-use data have been collected retrospectively, between November 2011 and December 2013, from centers experienced with the Spectra Optia System's WBCD procedure.

With this amendment, additional safety data will be collected for the 22-hour time period from 2 hours postapheresis until 24 hours postapheresis.

Specifically, the following new data will be collected:

1. Adverse event data for AEs that occurred during the 24-hour time period following the WBCD procedure (eg, date/time of start and end, ongoing, severity, action taken relationship to device/apheresis procedure/underlying disease/treatment for underlying disease, outcome, SAE, unexpected adverse device effect).

Note: The Investigator at each site will document his/her opinion of the relationship of the event to the procedures or underlying disease. The criteria below, in addition to good clinical judgment, should be used in determining relatedness.

Not Related: The event is clearly related to factors other than the study device and/or procedure(s), such as the subject's clinical state.

Possibly Related: The event follows a reasonable temporal sequence from the time of study treatment administration/ procedure, and/or follows a known response pattern to study device/procedure(s) but could have been produced by other factors, such as the subject's clinical state or other therapeutic interventions.

Probably Related: The event follows a reasonable temporal sequence from the time of study device/procedure(s) and cannot be reasonably explained by other factors, such as the subject's clinical state or therapeutic interventions.

Definitely Related: The event follows a reasonable temporal sequence from the time of study device/procedure(s), and follows a known response pattern, and cannot be reasonably explained by other factors. In addition, the event occurs immediately following study procedure(s), and/or improves on stopping the study procedure, and/or reappears on resumption of study procedure(s).

2. Blood products transfused during the 24-hour time period following the WBCD procedure (eg, reason [AE or underlying disease], blood product, number of units, date/time of start and end).
3. Postapheresis clinical laboratory results, as available (eg, prothrombin time [PT], international normalized ratio [INR], WBC count, platelet count, hematocrit, red blood cell count).

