## 2. SOURCE DATA

The original data capture system was Open Clinica with data management provided by Terumo BCT. As noted earlier, safety data were only collected through 2 hours post procedure. This data management system was retired shortly after database lock so it was not available for collection of additional safety data.

The additional safety data collected primarily consist of laboratory data and adverse event data through 24 hours post procedure. To further support a safety discussion in the CIR, additional data for blood products transfused will also be collected.

A new EDC system (Merge) was established, which contains much of the original data as well as the additional data. The following CRF pages were implanted into Merge:

- Adverse event
- Apheresis procedure (date, time, duration)
- Blood products transfused
- Laboratory data
- Medical history
- Concomitant medications

All analyses related to these CRF pages will be based solely on the new EDC. Some CRF pages from the original database were not expected to contribute to the additional safety information. Thus, analyses with respect to those CRF pages will continue to use data from Open Clinica. These CRF pages are:

- Demographics
- Vital signs
- Procedure Information (other than date, time, duration)
- Replacement fluids
- Device deficiencies

The additional safety data will only be collected at Sites 1 and 3. While Site 2 is not participating in the additional safety data collection, the corresponding data will be included in the Merge system in order to have a single database with key CRF pages. This avoids the situation where data from the same CRF come from different sources.

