Table 14.3.1.8.2	Treatment Emergent Adverse Events Related to Underlying Disease	Safety Analysis Set – 24 Hour Monitoring
Table 14.3.1.9.1	Treatment Emergent Adverse Events Related to Treatment of Underlying Disease	Safety Analysis Set – 2 Hour Monitoring
Table 14.3.1.9.2	Treatment Emergent Adverse Events Related to Treatment of Underlying Disease	Safety Analysis Set – 24 Hour Monitoring
Table 14.3.2	Summary of Blood Products Transfused	Safety Analysis Set

Listings:

Listing 16.2.1.1	Disposition	Safety Analysis Set
Listing 16.2.1.2	Demographics and Baseline Characteristics	Safety Analysis Set
Listing 16.2.1.3	Medical History	Safety Analysis Set
Listing 16.2.1.4	Prior and Concomitant Medication	Safety Analysis Set
Listing 16.2.1.5	Blood Products Transfused	Safety Analysis Set
Listing 16.2.1.6	Anticoagulants	Safety Analysis Set
Listing 16.2.1.7	Replacement Fluids	Safety Analysis Set
Listing 16.2.2.1	White Blood Cell Depletion	Full Analysis Set
Listing 16.2.2.2	White Blood Cells Processed	Full Analysis Set
Listing 16.2.2.3	Waste Bag CBC	Full Analysis Set
Listing 16.2.2.4.1	Pre/Post Procedure Lab Results	Full Analysis Set
Listing 16.2.2.4.2	Pre/Post Procedure Calcium Results	Full Analysis Set
Listing 16.2.2.4.3	Pre/Post Procedure Potassium Results	Full Analysis Set
Listing 16.2.2.4.4	Patients with Low Platelets	Full Analysis Set
Listing 16.2.3.1	Adverse Events	Safety Analysis Set
Listing 16.2.3.2	Adverse Events Leading to Discontinuation of Study Procedures	Safety Analysis Set
Listing 16.2.3.3	Serious Adverse Events	Safety Analysis Set
Listing 16.2.3.4	Vital Signs	Safety Analysis Set

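### The relatedness criteria are written for the device or procedure only but must also serve the disease and treatment attributions, and two 2-hour tables of those attributions include a site with no described collection

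*Protocol*

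**What the plan says.** Amendment 1.0, section 1.1, lists the relationship of adverse events to the underlying disease, or to treatment for it, among the new information to be collected. Section 2.4, item 1, then asks for four attributions per event: "relationship to device/apheresis procedure/underlying disease/treatment for underlying disease, outcome, SAE, unexpected adverse device effect".

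The note under that item sets the scope: "The Investigator at each site will document his/her opinion of the relationship of the event to the procedures or underlying disease". It goes on: "The criteria below, in addition to good clinical judgment, should be used in determining relatedness". Four categories follow, from Not Related to Definitely Related. The first is "Not Related: The event is clearly related to factors other than the study device and/or procedure(s), such as the subject's clinical state".

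SAP section 5 names the disease and treatment relationship as a new variable. SAP Appendix 1 reports it in Tables 14.3.1.8.1 and 14.3.1.8.2 (underlying disease) and in Tables 14.3.1.9.1 and 14.3.1.9.2, titled "Treatment Emergent Adverse Events Related to Treatment of Underlying Disease". In each pair the first table is for 2-hour monitoring and the second for 24-hour monitoring.

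On sites, SAP section 2 states: "The additional safety data will only be collected at Sites 1 and 3". Site 2's existing records are carried into the new database so that each form has a single source. SAP section 4 restricts the 24-hour adverse event tables to Sites 1 and 3. It sets no such limit on the 2-hour tables.

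**The concern.** The disease and treatment fields exist to help a reader of the 24-hour safety data separate effects of apheresis from effects of leukemia and chemotherapy. That needs a scale which can express relatedness to disease and to its treatment. The scale given has the device or procedure as its object throughout, and disease enters only as a rival explanation. Two sites that resolve this mismatch differently would produce codes that cannot be pooled, and the tables would not reveal it.

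The second problem is independent of the first. The two 2-hour tables use a variable for which the documents describe no source at Site 2, on an analysis set that is not limited by site. An event with no recorded attribution cannot be counted as related. If it stays in the denominator, it counts in effect as unrelated.

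**Working it through.** The plan gives no figure to reproduce for this point. The first part is a reading of the text; the second needs one line of algebra.

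**Part 1: do the criteria fit the four attributions?**

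1. Required attributions (Amendment 1.0, section 2.4, item 1): device, procedure, underlying disease, treatment for underlying disease.
2. Coding rule (note to the same item): one set of criteria plus clinical judgment. The note's scope sentence names procedures and underlying disease. It does not name treatment, although treatment is on the list to be collected.
3. The four categories, applied literally to an event clearly caused by the disease:

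| Category | Object of the definition | Role of other causes | Disease-caused event |
|---|---|---|---|
| Not Related | Device/procedure | Clinical state is the named example of another factor | Fits |
| Possibly Related | Device/procedure | Rival cause: "follows a known response pattern to study device/procedure(s) but could have been produced by other factors" | Fits only through its timing or response pattern relative to the procedure |
| Probably Related | Device/procedure | Exclusion: "cannot be reasonably explained by other factors, such as the subject's clinical state or therapeutic interventions" | Cannot fit |
| Definitely Related | Device/procedure, with timing or response to stopping or resuming it | Exclusion: no other factor may reasonably explain the event | Cannot fit |

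4. Count: 0 of 4 categories define relatedness to disease, and 0 of 4 define relatedness to its treatment. An event clearly caused by chemotherapy meets the same obstacle, since therapeutic interventions also appear only as a rival cause.
5. Is there another scale? Protocol sections 11.2 to 11.5 cover the adverse event definition, CTCAE grading, the serious event definition and the reporting window. Amendment section 1.1 announces the new attribution without criteria. The SAP addendum lists the variable and the tables without criteria. None of them gives a separate scale.
6. Outputs that depend on these fields: Tables 14.3.1.8.1, 14.3.1.8.2, 14.3.1.9.1 and 14.3.1.9.2. Tables 14.3.1.6.x (device) and 14.3.1.7.x (procedure) ask the question that the criteria were written for, so this mismatch does not touch them.

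**Part 2: Site 2 in the 2-hour tables**

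1. The attribution is new (Amendment section 1.1; SAP section 5).
2. New safety data come from Sites 1 and 3 only (SAP section 2), and Site 2 contributes its existing records.
3. The site restriction in SAP section 4 covers the 24-hour tables, so Tables 14.3.1.8.2 and 14.3.1.9.2 are already handled.
4. Tables 14.3.1.8.1 and 14.3.1.9.1 are listed on the Safety Analysis Set with 2-hour monitoring and no site limit.
5. Let p be the proportion coded as related at Sites 1 and 3, and s the share of the table's denominator that comes from Site 2. With Site 2 kept in the denominator and no attribution recorded there:

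   displayed proportion = p × (1 − s) + 0 × s = p × (1 − s)

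   With Site 2 left out, the displayed proportion is p. The relative shortfall is therefore s.
6. The documents give neither p nor s. They also do not say whether the denominator is events, patients or procedures. The direction follows for any p and s above zero; the amount cannot be computed.

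**The case against.** The strongest reply is that each definition states its own object. An event due to leukemia is correctly Not Related on the device or procedure question. It becomes Not Related to disease only if someone carries that answer into a different field, which an investigator using clinical judgment, as the note allows, would probably not do. The case report forms, their completion guide and SAP Version 1.0 are also not among the documents. The disease and treatment fields may be yes/no items, or may carry their own wording.

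Much of this stands. A reader might infer that the scale reads backwards and that every disease-caused event will be miscoded. The documents do not support that: judgment is allowed and the form is not shown. The reply does not remove the gap, though. The note puts underlying disease within its scope and sends the investigator to criteria that do not address it. Judgment then has to replace the criteria, and nothing visible makes two sites exercise it in the same way.

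On Site 2, it is fair to say that no text states how missing attributions will be displayed, and that SAP section 5 allows tables with insufficient data to be omitted. The understatement is therefore conditional on Site 2 remaining in the denominator. A reader might also want to attach a percentage to it. That would require an invented true rate, invented site shares and an assumed denominator.

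The consequence is limited as well. The study is descriptive, without formal hypothesis testing, and the white cell outcomes do not depend on these fields.

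**Conclusion.** The point holds as a defect of definition with a limited reach. Amendment section 2.4 prescribes criteria for relatedness to underlying disease that define relatedness only to the device or procedure, and it provides nothing for treatment of the disease. The expected effect is inconsistent coding between Sites 1 and 3 in the fields behind Tables 14.3.1.8.x and 14.3.1.9.x. Its frequency cannot be estimated from the documents. This rests on the assumption that the case report form and its guide contain no separate criteria; if they do, a citation in the SAP would settle this part.

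The Site 2 point also holds. Tables 14.3.1.8.1 and 14.3.1.9.1 include a site with no described source for the attribution, and they would understate it by the relative amount s if Site 2 is counted in the denominator. This rests on Site 2 not having supplied the new field, which follows from SAP sections 2 and 5 but is not stated outright.

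The change should be made: it is cheap, and the separation of causes is what these tables are for.

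**What to change.** - Reword the four definitions against the factor being assessed (device, procedure, underlying disease, or its treatment), with all remaining causes as the other factors. Alternatively, keep the present scale for device and procedure and use a yes/no attribution for disease and for treatment.
- Have Sites 1 and 3 confirm the disease and treatment fields already coded, under the revised wording.
- Restrict Tables 14.3.1.8.1 and 14.3.1.9.1 to Sites 1 and 3, as SAP section 4 already does for the 24-hour tables, or show Site 2 as not collected and outside the denominator.
- If a graded scale is kept for disease and treatment, state in the SAP which categories count as related, since the addendum does not.

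The cost is a paragraph of definitions, a short query round at two sites, and a filter or footnote in two tables. No device, procedure or white cell analysis changes.
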